2.2 Secondary

2.21 Median time to achieve MRD⁻ (negative) status (in blood and in bone marrow) after initiation of ibrutinib maintenance treatment.

2.22 Toxicity profile of ibrutinib as maintenance therapy after frontline induction.

2.23 Durability of the MRD⁻ state (determined from the time of first documentation of MRD⁻ until the first documentation of MRD⁺ (or last date shown to be MRD- for a censor)).

2.24 Time to requirement of next therapy for patients who achieve confirmed MRD⁻ vs. those who remain MRD⁺ disease at 48 weeks (end of 12 cycles).

2.25 Progression free survival (as determined by the IWCLL criteria) among patients who achieve confirmed MRD vs. those who remain MRD⁺ disease at 48 weeks (end of 12 cycles).

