8. Minimal residual disease: MRD assessment will be done at baseline, during the treatment phase and then during the observation phase (no treatment). The MRD will be done on peripheral blood and / or bone marrow aspirate using flow cytometry standardized Mayo Clinic panel. In general bone marrow aspirate evaluation will only be required when the peripheral blood is recorded at least twice (at two separate evaluation 3 months apart) to be negative. If blood is positive for MRD assessment, then bone marrow aspirate evaluation for the MRD will not be needed and can be deferred. **MRD assessment in the Blood:** (a) **Baseline:** all patients will have MRD assessed in the peripheral blood prior to initiating the study. (b) **During treatment phase:** all patients will have MRD assessed in the peripheral blood every 3 cycles. If the ibrutinib maintenance treatment is held > 21 days for toxicity or for any other reason(s) then the MRD testing will be delayed to accommodate 3 treatment cycles prior to testing. (c) **During observation period:** all patients will have MRD assessed within 4 weeks of completion of the last treatment cycles and thereafter every 3 months (if they are MRD negative) and every 6 months (if they are MRD+) for a maximum follow-up of 2 years or until initiation of subsequent treatment for relapsed disease (whichever happens first). **MRD assessment in the Bone marrow aspirate:** The schedule of assessment of the bone marrow aspirate for MRD will be different and dependent upon the results of the MRD status in the blood. (a) **Baseline:** If the peripheral blood MRD results are positive then a BM aspirate assessment for MRD will not be needed. If the peripheral blood MRD results are negative, then a BM aspirate assessment for MRD will be needed. (b) **During the treatment phase:** The MRD assessment of the Bone marrow aspirate will only be required once the peripheral blood MRD is recorded to be negative for at least 2 evaluations that are separated at least 3 months apart. If the blood evaluation demonstrates positivity for MRD, then Bone marrow aspirate evaluation will not be required and can be deferred until the peripheral blood is noted to be negative x 2. (c) **During the observation period:** The MRD assessment of the Bone marrow aspirate will only be required if the post treatment peripheral blood assessment (i.e., that done within 4 weeks of the last treatment dose) was noted to be negative. If the post treatment blood evaluation was noted to be positive, then no bone

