13.0 Treatment/Follow-up Decision at Evaluation of Patient

- 13.1 If the patient develops PD at any time during active treatment they will go to event monitoring. If the patient develops unacceptable adverse events, if the treating physician feels it is in the patient's best interest, or if the patient refuses all further study participation, study treatment will be discontinued, and the patient will go directly to event monitoring. Patients will then be followed in event monitoring per Section 18.0.
- 13.2 Patients not progressing on active treatment will continue treatment per protocol up to a maximum of 36 cycles. After the completion of 36 cycles, the patient will go to observation (maximum duration of observation 2 years). After completing observation, patients will enter event monitoring. NOTE: Patients who have residual disease at the end of 36 cycles will continue to event monitoring.
- 13.3 A patient is deemed ineligible if after registration, it is determined that at the time of registration, the patient did not satisfy each and every eligibility criteria for study entry. The patient may continue treatment off-protocol at the discretion of the physician as long as there are no safety concerns and as long as the patient was properly registered. The patient will go directly to the event-monitoring phase of the study (or off study, if applicable).
 - If the patient received treatment, all data up until the point of confirmation of ineligibility must be submitted. Event monitoring will be required per Section 18.0 of the protocol.
 - If the patient never received treatment, on-study material and the End of Active Treatment/Cancel Notification Form must be submitted. No further data submission is necessary.

Note: Due to the nature of the disease, if the patient is diagnosed with DLBCL within the first cycle of treatment, it will be assumed that the DLBCL was present at registration. The patient will be deemed ineligible per Sec 3.27.

- 13.4 A patient is deemed *cancel* if he/she is removed from the study for any reason before any study treatment is given. On-study material and the End of Active Treatment/Cancel Notification Form must be submitted. No further data submission is necessary.

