The analysis for this trial will commence at planned time points (see 16.2) and at the time the patients have become evaluable for the primary endpoint. Such a decision will be made by the Statistician and Study Chair in accordance with CCS Standard Operating Procedures, availability of data for secondary endpoints (e.g., laboratory correlates), and the level of data maturity. It is anticipated that the earliest date in which the results will

be made available via manuscript, abstract, or presentation format is when the last patient has been followed for at least 6 months.

16.31 Primary Endpoint:

- 16.311 Definition: The primary endpoint of this trial is the rate of confirmed MRD-negative response. A confirmed MRD-negative response is defined as an achievement of MRD-negative status in both the blood and the bone marrow on two consecutive evaluations at least 3 months apart. Confirmed MRD-negative response will be evaluated using all cycles of treatment. All patients meeting the eligibility criteria who have signed a consent form and have begun treatment will be evaluable for response, with the exception of patients who are determined to be a major treatment schedule violation.
- 16.312 Estimation: The proportion of successes will be estimated by the number of successes divided by the total number of evaluable patients. Ninety-five percent exact binomial confidence intervals for the true success proportion will be calculated.

16.32 Secondary Endpoint:

- 16.321 Duration of MRD-negative response is defined in patients who have achieved a confirmed MRD-negative response as the time from the earliest date that the patient was noted as having MRD-negative response in both the blood and bone marrow until the first notation of MRD positive disease in the blood or the bone marrow. The distribution of duration of MRD-negative response will be estimated using the method of Kaplan-Meier.⁵⁸
- 16.322 Time to MRD-negative response is defined in patients who have achieved a confirmed MRD-negative response as the time from the date of registration to the earliest date that the patient was noted as having MRD-negative response in both the blood and bone marrow. Time to MRD-negative response will be summarized descriptively (median, range).

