- 16.323 Time to requirement of next therapy: A landmark analysis will be conducted to evaluate time to requirement of next therapy for patients who achieve a confirmed MRD-negative response in both the blood and bone marrow vs. those who remain MRD-positive, as assessed at 48 weeks (end of 12 cycles; +/- 4 weeks). Patients who discontinue treatment before 48 weeks are excluded from this analysis. Time to requirement of next therapy will be defined as the time from the 48 week MRD evaluation until the time of initiation of subsequent treatment for progressive CLL. The distribution of time to requirement of next therapy will be estimated using the Kaplan-Meier method and log-rank statistics will be utilized to evaluate differences between the two groups.
- 16.324 Progression-free survival: A landmark analysis will be conducted to evaluate progression-free survival for patients who achieve a confirmed

MRD-negative response in both the blood and bone marrow vs. those who remain MRD-positive, as assessed at 48 weeks (end of 12 cycles; +/- 4 weeks). Patients who discontinue treatment before 48 weeks are excluded from this analysis. Progression-free survival will be defined as the time from the 48 week MRD evaluation until the time of disease progression per the IWCLL criteria or death due to any cause. The distribution of progression-free survival will be estimated using the Kaplan-Meier method and log-rank statistics will be utilized to evaluate differences between the two groups.

16.325 Adverse Events: Platelets and hemoglobin will be graded according to the Grading Scale for Hematologic Adverse Events in CLL Studies in Appendix V. The maximum grade for each type of adverse event, regardless of causality, will be recorded and reported for each patient, and frequency tables will be reviewed to determine adverse event patterns. Adverse events will continue to be recorded and reported up to 30 days after the last day of study drug treatment.

16.33 Correlative Analyses. The reports on the correlative will be descriptive as they are exploratory in nature.

16.332 Study of the impact of ibrutinib treatment on mood is exploratory in nature. Reports of these correlative analyses will be descriptive.

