| CRF | Event Monitoring Phase ¹ | | | | |
|------------------|---|--|--|-------|--------------------|
| | q. 3 months until PD or subsequent treatment for CLL ² | At PD or subsequent treatment for CLL ² | q. 6 mos. after PD or subsequent treatment for CLL | Death | New Primary |
| Event Monitoring | X | X | X | X | At each occurrence |

1. If a patient is still alive 5 years after registration, no further follow-up is required.
2. Submit copy of documentation of progression to the Operations Office, Attention: QAS for MC1481, [contact].

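### Duration of MRD-negative response ends only at a positive MRD test, so responders who die, progress without a prior positive test or start new CLL therapy may be censored rather than counted as failures

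*Combined protocol and SAP*

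**What the plan says.** Section 16.321 starts the clock when a confirmed responder is first negative in both blood and marrow and runs it "until the first notation of MRD positive disease in the blood or the bone marrow". It adds that "The distribution of duration of MRD-negative response will be estimated using the method of Kaplan-Meier". It gives no censoring rule. The only one is in goal 2.23: "or last date shown to be MRD- for a censor".

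Other sections determine when an MRD result can still arise:

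- Section 13.1: "If the patient develops PD at any time during active treatment they will go to event monitoring". Section 13.5 sends patients with DLBCL straight there too.
- The follow-up table in section 18.1 lists a single Event Monitoring form, due "q. 3 months until PD or subsequent treatment for CLL", at those events, and at death. It lists no MRD submission.
- Section 4.0, footnote 8, continues MRD testing in observation "for a maximum follow-up of 2 years or until initiation of subsequent treatment for relapsed disease (whichever happens first". Section 11.3(C) gives the same two limits.
- The section 4.0 schedule marks an MRD assessment at the Study Drug Discontinuation visit, and section 18.1 lists quantitative flow cytometry at end of treatment.

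By contrast, progression-free survival in section 16.324 runs "until the time of disease progression per the IWCLL criteria or death due to any cause".

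**The concern.** A responder can stop being in MRD-negative remission without a positive test. Examples are death between scheduled tests, nodal or organ relapse with negative blood, transformation, or new therapy begun before the next sample. Under 16.321 and 2.23 that patient contributes no event and leaves the risk set at the last negative test. Kaplan-Meier then treats the patient as having the same future chance of staying negative as those still followed. A reader would take the curve as the share of responders who remain in MRD-negative remission, and it does not estimate that.

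Durability is a named secondary goal. It is part of the third feature that section 1.3 gives for the study's uniqueness, and section 16.25 says duration of response will be weighed in any decision to terminate the study. Responders will be few, so the handling of one or two patients can change the reported curve.

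**Working it through.** **1. The plan's own figures.** The documents state no target or expected value for duration. The stated design figures do reproduce. The exact binomial probability of at least 4 successes in 32 is 0.0738, 0.3997, 0.7279 and 0.9069 at true rates of 0.05, 0.10, 0.15 and 0.20, against 0.07, 0.40, 0.73 and 0.91 in section 16.24. Duration does not enter that rule. At the 20% rate the expected number of responders is 32 × 0.20 = 6.4.

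**2. Which failures can escape.**

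- *Blood-based progression* (11.214, and the clone-recurrence part of 11.216) needs a lymphocyte count of about 5,000/mm³ or more. The MRD threshold is one CLL cell per 10,000 leukocytes, with blood tested every three cycles on treatment and every three months in observation while negative. Such patients would normally test positive at or before progression.
- *Nodal, liver or spleen progression, and transformation* (11.211 to 11.213) need no positive blood or marrow result.
- *Death* between tests gives no MRD result.
- *New CLL therapy* ends MRD testing in observation.

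**3. Direction.** Let λ₁ be the hazard of a positive MRD test, and λ₂ the hazard of progression, new therapy or death without a prior positive test, both taken as constant.

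- Target of the plan's curve at time t: exp(−λ₁t).
- Proportion alive, progression-free, untreated and MRD-negative: exp(−(λ₁+λ₂)t).
- Ratio of the first to the second: exp(λ₂t). It is 1 when λ₂ = 0 and above 1 otherwise.

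One small-sample detail: the plan censors at the last negative test, slightly before the failure date. If another patient turns positive in that short interval, the plan's curve can briefly dip below the composite curve. The order is restored at the failure date.

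**4. Size, on assumed rates.** None of these hazards is in the documents. Take λ₁ = 0.20 per year and t = 2 years. The plan's target is exp(−0.40) = 0.670.

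| λ₂ per year (assumed) | Composite at 2 years | Plan's target |
|---|---|---|
| 0 | exp(−0.40) = 0.670 | 0.670 |
| 0.05 | exp(−0.50) = 0.607 | 0.670 |
| 0.10 | exp(−0.60) = 0.549 | 0.670 |
| 0.15 | exp(−0.70) = 0.497 | 0.670 |

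**5. Effect in a sample this small.** Take six hypothetical responders: MRD-positive at 12 and 21 months; a death at 10 months, last negative at 9; a progression with new therapy at 16 months, last negative at 15; two still negative at 24 and 27 months.

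- Plan's rule: 4/5 × 2/3 = 0.53 after 21 months.
- Death and progression or new therapy counted: 5/6 × 4/5 × 3/4 × 2/3 = 0.33.

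**The case against.** A reader might infer that MRD testing always stops at progression, so that no progressor can ever record an event. The documents do not support that. An MRD assessment is scheduled at the Study Drug Discontinuation visit, so a patient who progresses on treatment can still be recorded as positive. In observation, testing is stated to stop at two years or at new therapy, not at progression. The schema does send progression at any time to event monitoring, where no MRD form is listed, so testing after progression in observation is unclear. Blood-based progression would usually be MRD-positive first. All this narrows the affected group; it leaves deaths, failures with negative blood, and new therapy started before a positive test.

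A reader might also take 67% against 61%, 55% or 50% as measured bias from informative censoring. It is not. The hazards are assumed independent, and under independence Kaplan-Meier is unbiased for its own target of 67%. The gap is between two estimands.

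The sponsor can fairly say that time to MRD-positivity is a legitimate quantity, and that sections 16.323 and 16.324 already analyse next therapy, progression and death. The first point stands only if the plan states that this is the quantity wanted and treats the other failures as competing events. The second is partial: those are 48-week landmark analyses, exclude patients who stop treatment earlier, and do not follow later responders as responders.

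A bare list of four events would also be flawed. Patients who leave for toxicity or refusal are followed for progression and death but not MRD. Counting a late event at its own date would credit untested time as MRD-negative and could itself lengthen duration.

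**Conclusion.** The point holds as a gap in the definition of a secondary endpoint. With a positive MRD result as the only event and censoring at the last negative test, the curve does not estimate how long responders stay in MRD-negative remission. Its target is never lower than the proportion alive, progression-free, untreated and MRD-negative, and is higher whenever failures occur without a prior positive test. That ordering needs no particular rate.

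The size cannot be derived from the documents. It is zero if every failure is preceded by a positive test. On the assumed hazards above it reaches 17 percentage points at two years (67% against 50%), but the upper rates may be too high given how many progressors should test positive first. A reader should not conclude that durability will be materially overstated, only that the plan allows it and that one or two patients among about six could matter. The primary endpoint and the rule of 4 or more successes in 32 are unaffected.

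**What to change.** In 16.321, with 2.23 aligned to it:

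- Define the end of MRD-negative response as the earliest of a positive MRD result in blood or marrow, IWCLL progression, start of next CLL therapy, or death.
- Censor patients free of all four at their last MRD test, and state that date in 16.321 itself.
- Also censor at the last MRD test when the event follows a prespecified gap in testing, for example two or more missed scheduled assessments. Add a sensitivity analysis that counts those events.
- If pure MRD relapse is wanted as well, report its cumulative incidence with the other three as competing events.

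The cost is wording. The Event Monitoring form in section 18.1 already covers progression, subsequent treatment and death, and no procedure or sample size changes. The downside is that the reported duration may be shorter.

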6.2 Registration to the Correlative Research

Mandatory:

A mandatory correlative research component is part of this study, the patient will be automatically registered onto this component (see Sections 3.13, 4.0, 14.0 and 17.0).

6.3 Prior to accepting the registration, registration/randomization application will verify the following:

- IRB approval at the registering institution
- Patient eligibility
- Existence of a signed consent form
- Existence of a signed authorization for use and disclosure of protected health information

6.4 Documentation of IRB approval must be on file in the Registration Office before an investigator may register any patients.

In addition to submitting initial IRB approval documents, ongoing IRB approval documentation must be on file (no less than annually) at the Registration Office ([contact]). If the necessary documentation is not submitted in advance of attempting patient registration, the registration will not be accepted, and the patient may not be enrolled in the protocol until the situation is resolved.

When the study has been permanently closed to patient enrollment, submission of annual IRB approvals to the Registration Office is no longer necessary.

- 6.5 At the time of registration, the following will be recorded:
 - Patient has/has not given permission to store and use his/her sample(s) for future research of CLL at Mayo Clinic.
 - Patient has/has not given permission to store and use his/her sample(s) for future research to learn, prevent, or treat other health problems.
 - Patient has/has not given permission for MCCC to give his/her sample(s) to researchers at other institutions.
- 6.6 Treatment on this protocol must commence at Mayo Clinic under the supervision of a medical oncologist or hematologist.
- 6.7 Treatment cannot begin prior to registration and must begin \leq 14 days after registration.
- 6.8 Pretreatment tests/procedures (see Section 4.0) must be completed within the guidelines specified on the test schedule.
- 6.9 All required baseline symptoms (see Section 10.6) must be documented and graded.
- 6.9a Study drug is available on site.
- 6.9b **Patient Questionnaire booklets**
Patient questionnaire booklets are available on site. Copies are not acceptable for these submissions. Booklets should be ordered using the Patient Questionnaire Order Form.

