16.211 **Final Decision Rule:** Enter 32 evaluable patients into the study. If 3 or fewer successes are observed in the first 32 evaluable patients, we will consider this regimen ineffective in this patient population and terminate this study. Otherwise, if the number of successes is at least 4, this will be considered evidence of promising activity and the treatment may be recommended for further testing in subsequent studies.

16.212 **Over Accrual:** If more than the target number of patients are accrued, then the additional patients will not be used to evaluate the stopping rule or used in any decision making process. Analyses involving over accrued patients are discussed in Section 16.34.

16.22 **Sample Size:**

The phase II study design to be used is fully described in section 16.21. A maximum of 32 evaluable patients will be accrued onto this phase II study unless undue toxicity is encountered. We anticipate accruing an additional 3 patients to account for ineligibility, cancellation, major treatment violation, or other reasons. Maximum projected accrual is 35 patients.

16.23 **Accrual Rate and Study Duration:** The anticipated accrual rate is approximately 1-2 patients per month. Therefore, the accrual period for this phase II study is expected to be about 2 years. The final analysis can begin approximately 2.5 years after the trial begins, i.e. as soon as the final patient accrued to this trial has been followed for at least 6 months.

16.24 **Power and Significance Level:** Assuming that the number of responses is binomially distributed, with a significance level of 7%, the probability of declaring that the regimen warrants further studies (i.e., statistical power) can be tabulated as a function of the true success proportion as shown in the table below.

| If the true success proportion is... | 0.05 | 0.10 | 0.15 | 0.20 |
|--|------|------|------|------|
| Then the probability of declaring that the regimen is promising and warrants further study is... | 0.07 | 0.40 | 0.73 | 0.91 |

16.25 **Other Considerations:** Toxicity, quality/duration of response, and patterns of treatment failure observed in this study, as well as scientific discoveries or changes in standard care will be taken into account in any decision to terminate the study.

16.3 **Analysis Plan:**

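### Section 16.322 reports time to MRD-negativity only in confirmed responders, from registration and without censoring, so the median can be too short if the analysis runs at the earliest planned date

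*Combined protocol and SAP*

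**What the plan says.** Goal 2.21 asks for the median time to MRD-negative status in blood and marrow "after initiation of ibrutinib maintenance treatment". It names no denominator and does not say confirmed.

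Section 16.322 makes this operational: "Time to MRD-negative response is defined in patients who have achieved a confirmed MRD-negative response as the time from the date of registration", ending at the earliest date on which blood and marrow were both negative. The summary is a median and range. No censoring or competing-event rule is given. By contrast, Section 16.321 uses Kaplan-Meier for duration of MRD-negativity.

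A confirmed response (16.311) requires "MRD-negative status in both the blood and the bone marrow on two consecutive evaluations at least 3 months apart", judged over all cycles of treatment. In Section 4.0, footnote 8, "all patients will have MRD assessed in the peripheral blood every 3 cycles", and an on-treatment marrow is required only after two negative blood results at least 3 months apart. Section 7.1 allows up to 36 cycles of 28 days.

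Section 16.23 expects about 2 years of accrual and lets the final analysis begin at about 2.5 years, "as soon as the final patient accrued to this trial has been followed for at least 6 months". Section 16.3 ties the timing partly to data maturity.

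**The concern.** A patient enters the 16.322 summary only after confirmation. A patient enrolled shortly before the data cut can therefore contribute an early response or nothing. One who would convert in the second or third year is absent rather than censored. The responders visible at an early cut are then weighted towards short times, and a raw median has no means of correcting this. If the figure were read as the time ibrutinib maintenance takes to clear residual disease, it would look faster than it is.

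The start date also differs from the goal: registration in 16.322, initiation of ibrutinib in 2.21.

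**Working it through.** **Plan's own figures.** The plan gives no number for this endpoint. Its design table (16.24) reproduces: P(X ≥ 4 of 32) = 0.0738, 0.3997, 0.7279 and 0.9069 at 5%, 10%, 15% and 20%, against 0.07, 0.40, 0.73 and 0.91 printed. Nothing below touches that test.

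**Timing from the documents.**
- Maximum treatment: 36 × 28 = 1008 days; 1008 / 30.44 = 33.1 months.
- Follow-up at the 30-month cut: 6 to 30 months, or 26 to 130.5 weeks. No patient can have completed 36 cycles.
- Counting on-treatment blood tests only, the first required marrow falls at about cycle 6 (168 days, 5.5 months) and confirmation at about cycle 9 (252 days, 8.3 months). It could be earlier if blood was already negative at baseline or a marrow was taken for clinical reasons.
- Share of patients followed for less than 9 cycles, under uniform accrual: (8.28 − 6) / 24 = 9.5%, about 3 of 32.

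**Effect on the median.** Assumptions: uniform accrual; first joint negativity at week 24, 36, …, 132; confirmation 12 weeks later (three cycles taken as meeting the 3-month rule); response time unrelated to enrolment date. The chance that a responder with first negativity at week t is visible at the cut is

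S(t) = max{0, [130.5 − (t + 12)] / 104.5}.

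This gives 0.904, 0.789, 0.675, 0.560, 0.445, 0.330, 0.215, 0.100, 0 and 0. S(t) never rises with t, so the visible median can equal the full median or fall below it, but cannot exceed it.

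| Assumed conversion | Full median (weeks) | Visible median (weeks) | Shortening (weeks) | Eventual responders visible |
|---|---|---|---|---|
| Even over the ten visits | 78 | 48 | 30 | 40% |
| 10% per visit | 60 | 36 | 24 | 49% |
| 20% per visit | 48 | 36 | 12 | 59% |
| 30% per visit | 36 | 36 | 0 | 67% |

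For the even case, the S(t) sum to 4.02, so 40% are visible. Their cumulative share is 42% by week 36 and 59% by week 48, hence a median of 48. The full median lies midway between weeks 72 and 84. Medians move in 12-week steps, and the 10% case is on an edge: 50.2% of visible responders are at or before week 36, so 48 weeks would be nearly as fair a reading.

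**Counts.** At the 20% target, 0.20 × 32 = 6.4 responders are expected. In the even case 6.4 × 0.40 = 2.6 of them would be visible at the cut.

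**Time origin.** Section 6.7 allows at most 14 days from registration to treatment: 14 / 84 = one sixth of an assessment interval.

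**The case against.** Several points on the other side stand.

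- A reader might infer that 16.322 fails to answer goal 2.21. The documents do not support that. The goal names no denominator, and time to a status among those who reach it is a legitimate conditional reading. An all-patient median would almost surely not exist at the target rate: P(X ≥ 16 of 32) is 0.0001 at 20%.
- A reader might infer that the plan hides non-responders. It does not: Section 16.312 reports successes over all evaluable patients with an exact 95% interval.
- A reader might infer that the median will be cut short. That is conditional. Section 16.23 says when the analysis can begin, Section 16.3 lets timing follow data maturity, and all treatment cycles count. If the summary waits until treatment is complete, the truncation is gone.
- The size rests on conversion patterns that the documents do not give, and early conversion produces no shortening.
- The origin mismatch is numerically small, and the go/no-go rule does not use this median.

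What the objection does not remove is that no minimum follow-up is set for this summary, and that the 30-month date is the plan's own earliest schedule.

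**Conclusion.** The point holds in conditional form. The 16.322 median is a valid description of confirmed responders, but it has no protection against an early cut. At about 30 months it is either right or too short: by none at 30% conversion per visit, 12 weeks at 20%, 24 weeks at 10%, and 30 weeks with even spread. These sizes assume uniform accrual, a 12-week confirmation lag and the stated conversion patterns. The start-date mismatch is at most 14 days and is a matter of wording. This is a worthwhile improvement to a secondary endpoint and no threat to the primary analysis.

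**What to change.** In Section 16.322:

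1. Start the clock at first dose, to match goal 2.21.
2. Keep the median and range, labelled as conditional on confirmed response.
3. Add the cumulative incidence (Aalen-Johansen) of confirmed MRD-negativity in all evaluable patients. Stopping ibrutinib without confirmed response, progression and death are competing events; ongoing patients are censored at their last MRD test.
4. Date the event in this curve at the confirming evaluation, so that a patient with an unconfirmed first negative result is simply censored.
5. Report the curve with 95% confidence intervals at the end of cycles 6, 12 and 24. Add cycle 36 only once patients have been followed that long: it falls at week 144, beyond the 130.5-week maximum at the 30-month cut. With events dated at confirmation, expect the cycle 6 value to be close to zero on the required marrow schedule.

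The cost is SAP wording and one extra secondary estimate from data already collected. The estimate will be imprecise: about 6 responders are expected at the 20% target, and at the 30-month cut only about 32 × (130.5 − 96) / 104.5 = 10.6 patients would have 24 cycles of follow-up, before any dropout. The primary test is unchanged.

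### Time to next therapy (16.323): handling of death before next therapy is not stated, and the default Kaplan-Meier curve, read as a proportion, would modestly overstate need for therapy

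*Combined protocol and SAP*

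**What the plan says.** Section 16.323 defines a landmark comparison of confirmed MRD-negative with MRD-positive patients at 48 weeks. Time runs from the 48-week MRD evaluation "until the time of initiation of subsequent treatment for progressive CLL". On estimation it says: "The distribution of time to requirement of next therapy will be estimated using the Kaplan-Meier method". On comparison: "log-rank statistics will be utilized to evaluate differences between the two groups". On the population: "Patients who discontinue treatment before 48 weeks are excluded from this analysis".

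Death is not named in 16.323 as an event, a competing event or a reason for censoring, and the section gives no censoring rule. Goal 2.24 adds nothing on this. Neither competing risks nor cumulative incidence is mentioned anywhere in the document.

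Two neighbouring endpoints are more explicit. Progression-free survival in 16.324 uses the same landmark groups and time origin and runs "until the time of disease progression per the IWCLL criteria or death due to any cause". Goal 2.23 states a censoring date for durability of MRD negativity. Section 18.1 collects death in event monitoring and ends follow-up of survivors 5 years after registration.

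**The concern.** A patient who dies without starting new CLL therapy can never have the event. If Kaplan-Meier is run with treatment start as the only event, the patient can leave the risk set only by censoring. The method then treats the patient as exchangeable with those still at risk of starting therapy. One minus Kaplan-Meier answers a hypothetical question (how many would need therapy if nobody could die first), not how many patients in the group went on to need it.

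Goal 2.24 compares this endpoint by MRD status. Section 1.3 reports that MRD level predicts overall survival, so unequal death rates between the two groups are plausible on the trial's own rationale. The two curves could then be shifted by different amounts, and a reader who takes them as proportions would be misled about both the level and the difference.

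**Working it through.** The plan gives no figure for time to next therapy, so there is nothing to reproduce. The check is whether the direction of the bias follows from the method, and how large it could be.

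**Inputs from the documents**
- Event, estimator and test: 16.323.
- Maximum accrual: 35 (16.22).
- Earliest final analysis: about 2.5 years after the trial begins (16.23).
- Follow-up cap: 5 years from registration (18.1).
- Landmark: 48 weeks = 336/365.25 = 0.92 years.

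**Time after the landmark**
- Earliest final analysis, first patient: 2.5 - 0.92 = 1.58 years. Everyone registered later has less.
- Follow-up cap: 5 - 0.92 = 4.08 years.

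**Assumptions (not in the documents)**
- Constant annual hazards: next therapy a = 0.05 to 0.20; death without next therapy d = 0.02 to 0.05.

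**Formulas**
- One minus Kaplan-Meier with deaths censored: 1 - exp(-a t).
- Cumulative incidence with death competing: a/(a+d) × [1 - exp(-(a+d) t)].

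**Results**

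| a | d | t (years) | 1-KM | Cumulative incidence | Overstatement (points) |
|---|---|---|---|---|---|
| 0.05 | 0.02 | 1.58 | 7.6% | 7.5% | 0.1 |
| 0.20 | 0.05 | 1.58 | 27.1% | 26.1% | 1.0 |
| 0.05 | 0.02 | 4.08 | 18.5% | 17.7% | 0.7 |
| 0.10 | 0.02 | 4.08 | 33.5% | 32.3% | 1.2 |
| 0.10 | 0.05 | 4.08 | 33.5% | 30.5% | 3.0 |
| 0.20 | 0.05 | 4.08 | 55.8% | 51.2% | 4.6 |

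One row in full (a = 0.10, d = 0.05, t = 4.08): 1 - exp(-0.408) = 0.335; (0.10/0.15) × [1 - exp(-0.612)] = 0.667 × 0.458 = 0.305.

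**Effect on the group comparison.** Let both MRD groups have a therapy hazard of 0.10, with death hazards of 0.02 and 0.05. At 4.08 years Kaplan-Meier shows 33.5% in both. The true proportions are 32.3% and 30.5%, a difference of about 1.7 points before rounding.

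**When the bias is zero.** Take 10 patients, 3 starting therapy and 2 dying untreated, the rest followed throughout. The true proportion is 30.0%.
- Both deaths first: 1 - (7/8)(6/7)(5/6) = 37.5%.
- Order therapy, death, therapy, death, therapy: 1 - (9/10)(7/8)(5/6) = 34.4%.
- Both deaths after the last therapy start: 1 - (9/10)(8/9)(7/8) = 30.0%, no bias.

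One minus Kaplan-Meier is therefore never below the cumulative incidence, and exceeds it only if an untreated death precedes a later therapy start.

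**Set against sampling error.** For a proportion of 33.5%, the binomial standard error with all 35 patients in one group is √(0.335 × 0.665/35) = 8.0 points. The landmark groups must be smaller. At the design success rate of 20%, 0.20 × 32 = 6.4 patients are confirmed MRD-negative at any time; with 6 patients the standard error is √(0.335 × 0.665/6) = 19.3 points.

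**The case against.** The strongest reply is that the plan never commits the misuse. Section 16.323 promises an estimated distribution and a log-rank test; it does not promise to report one minus Kaplan-Meier as the share needing therapy. Goal 2.24 is a comparison over time, and the log-rank test makes it validly on the cause-specific hazard. Deaths are not hidden either, because 16.324 counts them in the same groups from the same origin. The size rests on assumed rates, and most patients will have far less than 4.08 years after the landmark at the first analysis.

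Most of this stands, and it rules out several stronger readings that a reader might infer:
- That the plan prescribes censoring at death. It does not; censoring is the default consequence of the stated event and estimator, and no rule is written.
- That the MRD comparison is invalid. It is not; the planned test is unaffected.
- That 16.323 and 16.324 contradict each other. They are different endpoints and may treat death differently; what is missing is a statement for 16.323.
- That the distortion is large. The documents give no rates to support that, and under the assumptions shown it lies within one standard error.

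What remains is that the rule for death is unstated, and that a Kaplan-Meier curve of time to next therapy is easily read as a proportion.

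**Conclusion.** The point holds as a minor gap in specification for one secondary endpoint. The direction of the bias follows from the method and needs no assumption about rates, only that deaths are censored, the curve is read as a proportion, and at least one untreated death precedes a later therapy start. Its size, about 0.1-1.0 points at the earliest final analysis and 0.7-4.6 points at the follow-up cap, depends entirely on the assumed constant hazards. With few deaths it would be about a point or less. The primary endpoint and the rule of at least 4 successes in 32 do not depend on it.

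**What to change.** In 16.323, replace the Kaplan-Meier estimate with the cumulative incidence of next therapy in each landmark group (Aalen-Johansen), with death before next therapy as a competing event. Show the cumulative incidence of death beside it: a group with higher mortality can appear to need less therapy simply because more of its patients die first. Keep the log-rank test and label it a test of the cause-specific hazard of starting next therapy.

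This takes a sentence or two and standard software. It needs no new data, since event monitoring already records deaths. The cost is one more curve per group, and the change will be slight if deaths are few. Writing the rule now also avoids choosing how to treat deaths after the data are seen.
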